The primary objective of this pilot study is to determine the feasibility and effectiveness of a COVID-19 screening program for passengers departing from YVR. This research study is conducted by The University of British Columbia (UBC) and Providence Health Care, sponsored by WestJet and Vancouver Airport Authority. The experimental study investigates point-of-care rapid test device for detecting SARS-CoV-2, the virus responsible for COVID-19. The study is investigating a method of rapid-testing for COVID-19 and will help inform the safest and most efficient way of testing departing passengers prior to security screening at Vancouver International Airport (YVR). This study is also evaluating a new passenger management system.

Summary of the Research Proposal

Purpose:

The purpose of this pilot study is to determine the feasibility and effectiveness of a COVID-19 screening program at YVR for WestJet and KLM passengers.

Hypothesis:

SARS-CoV-2 infection can be effectively screened using point-of-care rapid antigen assays.

Justification:

Passengers are required to wear masks and physically distance while traveling by air. However, the majority of general public is still worried about the potential risk of contracting COVID-19 on airplanes, especially during long flights. We need to develop methods and strategies to quickly screen for SARS-CoV-2 infection, prior to boarding flights.

Objectives:

1. To develop and deploy a management algorithm for COVID-19 screening at YVR that will involve the use of point-of-care rapid test device.
2. To evaluate the acceptability of such screening algorithm and determine the costs of deploying the program.

Research Design:

Study Population: Working in collaboration with WestJet and KLM we will invite all passengers meeting Inclusion/Exclusion on outbound flights from YVR Airport to participate in this study.

Phase 1: We will work with YVR and WestJet to enroll 200 subjects into the study. For this initial phase we are looking to determine the rate of positivity in the cohort. This initial phase is needed to evaluate the feasibility of this pilot program and to refine the initial management algorithm. Health Canada-approved Panbio Covid-19 Ag Rapid Test Device by Abbott Rapid Diagnostics (approved for Lab-based test and Point of care test on 2020-10-05) will be used in Phase 1.

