Phase 2: Strategies for achieving higher-throughput will be determined after completion of Phase 1. In phase 2, we will continue to work with YVR and WestJet, with the addition of KLM, to enroll 700 subjects into the study. Phase 2 will further assess the efficiency of our COVID-19 screening and passenger management algorithm.

The study is purposefully designed to be as minimally invasive to the passengers' travel plan as possible. The Study Plans for Phase 1 and Phase 2 are detailed below.

Statistical Analysis:

- When we aggregate the data for analysis, we will use basic statistics to determine mean, variance, standard deviation, and positivity rate...etc.

INVESTIGATIONAL PLAN

Phase 1 Recruitment

Inclusion Criteria:

1. The subject must be between 19 and 80 years of age.
2. The subject must be a resident of B.C.
3. The subject must have a ticket to board a WestJet flight departing from Vancouver International Airport (YVR).
4. Have a minimum of 75 minutes of free time prior to the scheduled flight's departure.

Exclusion Criteria:

1. We will exclude subjects who have previously tested positive for COVID-19 within the past 90 days
2. We will exclude subjects who cannot provide written informed consent

Phase 2 Recruitment

Inclusion Criteria:

1. Subject has access to accommodation in Canada for safe-isolation as per public health guidelines
2. Between the ages of 13 – 90
3. Travelling on any WestJet or KLM flight
4. Have a minimum of 70 minutes (if travelling within Canada) or 90 minutes (if travelling International) of free time prior to the schedule flight's departure

Exclusion Criteria:

1. We will exclude subjects who have previously tested positive for COVID-19 within the past 90 days
2. We will exclude subjects who cannot provide written informed consent or assent

Onsite Recruitment

For Phase 1, we will approach eligible passengers arriving at YVR terminal between 8 AM and 12 PM noon. For Phase 2, we will approach eligible passengers arriving at YVR terminal between 6:30 AM and 10:30 AM to capture WestJet's largest carrier departing at 9 AM, and between 11:30 AM and 3:30 PM on Thursday and Sunday for KLM flights. We will also mention a discount coupon will be given to WestJet passengers who successfully complete the study.

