- Study Coordinator stationed here with YVR staff (all wearing masks and are able to maintain appropriate distance)
- Study banners stationed here, with high-level details including steps and eligibility criteria (see “Banners”).
- Appropriate distancing markers on the floor to remind study participants to maintain distance while waiting in line
- Welcome Package: bottled water, pens, brochure (see “General Brochure”), and basic study plan (no informed consent form)
- Have alcohol-based hand rub (ABHR) station available to facilitate hand hygiene
- Provide a mask if passenger is not wearing mask
- Check basic inclusion/exclusion criteria
- Answer basic questions about the study
- Inform the risk of denied boarding, if screened positive
- If interested, direct to Informed Consent Area or Citizen Care Pod (5 stations) or wait inside terminal (5 seats allowing physical distancing with dividers)

Citizen Care Pod

- Passenger (potential study subject) will sanitize hands upon entry
- Potential study subject will sit at 1/5 station, facing curb-side side (these 5 stations will have partitions between participants as a physical barrier)
- Clinical Coordinator (all wearing PPE – gown, mask, shield, and gloves, more details below) will come up behind the subject to go through the informed consent
- Once signed consent form, proceed to collect NP swab and oral rinse
- Make sure the subject has no signs of bleeding after NP swab, and rest
- The subject will be given a questionnaire and directed outside of the Care Pod
- Another hand sanitization station will be available for subjects as they exit

Rapid COVID-19 Testing On Site

- For Phase 1, only the NP swab sample will be tested on site using the rapid test device. If the sample is positive, “Positive Screen Test Results” Protocol will be followed (see below). The remaining NP swab sample and oral rinse sample will be transferred back to research laboratory for confirmatory RT-PCR testing.
- For Phase 2, both the NP swab sample and the oral rinse sample will be tested on site using two separate rapid test devices. If either sample is positive, “Positive Screen Test Results” Protocol will be followed (see below). The remaining samples will be transferred back to research laboratory for confirmatory RT-PCR testing.

Results Office

- Results Office – a private room inside the YVR terminal

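### Does the unqualified positivity rate blend two different definitions of a positive screen?

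*Protocol*

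**What the plan says.** The protocol has one sentence on analysis, in the Statistical Analysis paragraph of the Summary of the Research Proposal. It follows the descriptions of both phases: "When we aggregate the data for analysis, we will use basic statistics to determine mean, variance, standard deviation, and positivity rate...etc".

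The section Rapid COVID-19 Testing On Site sets a different screening rule for each phase. "For Phase 1, only the NP swab sample will be tested on site using the rapid test device". "For Phase 2, both the NP swab sample and the oral rinse sample will be tested on site using two separate rapid test devices". In Phase 2 the positive-result procedure starts "If either sample is positive". In both phases what is left of the samples goes for RT-PCR; for Phase 2 the text is "The remaining samples will be transferred back to research laboratory for confirmatory RT-PCR testing".

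A positivity rate is named as a target in one other place, Research Design, where it belongs to Phase 1: "For this initial phase we are looking to determine the rate of positivity in the cohort". The aim given there for Phase 2 is different: to assess further how efficient the screening and passenger management are.

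Eligibility also differs. Phase 1 takes B.C. residents aged 19 to 80 on WestJet. Phase 2 takes ages 13 to 90 on WestJet or KLM, requires access to accommodation in Canada for isolation, and lists no B.C. residence criterion.

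**The concern.** The same two words can stand for two quantities. Adding a second specimen under an either-positive rule can raise the share of screen positives with infection unchanged, partly through extra true positives and partly through extra false positives. If all subjects were put into one numerator and one denominator, the result would describe neither screening rule and would also mix two populations.

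This would matter because the stated hypothesis is "SARS-CoV-2 infection can be effectively screened using point-of-care rapid antigen assays". A reader could take a higher Phase 2 or combined figure as more infection or better detection when it came from the change of rule. A single rate would not show whether the oral rinse adds true positives, false positives or both.

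**Working it through.** The protocol states no expected rate, precision target or derivation of its sample sizes, so there is no figure of its own to reproduce.

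**Inputs from the protocol.** Planned enrolment is 200 in Phase 1 and 700 in Phase 2 (Research Design). A positive screen is one NP test in Phase 1 and either of two tests in Phase 2 (Rapid COVID-19 Testing On Site).

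**Mixture weights.** 200/900 = 22.2% and 700/900 = 77.8%.

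**Assumed inputs.** Prevalence p = 0.5%, sensitivity Se = 80%, specificity Sp = 99.5%, equal for both specimens and both phases. None of these is in the protocol.

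**Formulas and results.**

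- Phase 1 rule: p·Se + (1 − p)(1 − Sp) = 0.00400 + 0.004975 = 0.90%.
- Phase 2 rule, independent errors: p[1 − (1 − Se)²] + (1 − p)(1 − Sp²) = 0.00480 + 0.009925 = 1.47%.
- Phase 2 rule, fully coincident errors: the same as one test, 0.90%.
- Pooled rate, independent errors: (200 × 0.8975% + 700 × 1.4725%)/900 = 1.34%. With coincident errors it is 0.90%.

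In the independent case the pooled rate is 1.47 − 1.34 = 0.13 points below the Phase 2 rate and 1.34 − 0.90 = 0.45 points above the Phase 1 rate (0.447 before rounding). In the coincident case both gaps are zero.

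**Comparison with sampling error.** The independent case expects 900 × 1.34% ≈ 12 screen positives overall and 200 × 0.8975% ≈ 1.8 in Phase 1. The exact 95% interval for 12/900 is 0.7% to 2.3%, which contains both phase rates. For 2/200 it is 0.1% to 3.6%.

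**Sensitivity to the assumptions.** Take prevalence 0.1% to 1%, sensitivity 50% to 90%, specificity 98% to 99.9% and independent errors. The Phase 2 rate is then about 1.2 to 2.0 times the Phase 1 rate in the same population. At the low-specificity end (p = 0.1%, Se = 50%, Sp = 98%) the rates are 2.05% for Phase 1, 4.03% for Phase 2 and 3.59% pooled. With fully coincident errors the ratio is 1.0 throughout.

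**Does the text call for pooling?** Aggregating data to obtain means, variances and rates can simply mean summarising individual records. The one place that says whose positivity is wanted names the Phase 1 cohort, and Phase 2 has its own aim. If positivity means RT-PCR positivity, the change in the rapid-test rule does not affect the rate in the same way.

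**Would the data allow a proper breakdown?** Yes. Phase 2 uses a separate device for each specimen, and remaining samples go for RT-PCR in both phases. The NP result exists in both phases as a common measure, provided the device is the same; the protocol names it for Phase 1 only ("Point of care test on 2020-10-05) will be used in Phase 1").

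**The case for a change.** The best case for a change is that this is more than missing detail. The protocol names a single outcome rate, changes the event behind it between phases and never reconciles the two. Nor does the problem depend on pooling alone: two phase rates side by side cannot separate a change in infection from a change in rule or population. A positive screen carries a risk of denied boarding, so it matters whether added positives are true. In the independent case above, the rise from Phase 1 to Phase 2 is 0.575 points before rounding, of which 0.495 are false positives (86%). The remedy would be wording only.

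Much of this is correct. The rate is undefined in the sentence, the rules do differ, and a pooled screen-positive rate would be hard to interpret. At low specificity with independent errors the gap between the pooled and Phase 1 rates would not be small.

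It does not show that the plan is wrong. The false-positive share, and the fall in predictive value that goes with it, result from the either-positive rule and would occur however the rate is reported. Side-by-side rates without specimen results would be uninformative, but nothing in the protocol says that specimen results will be merged. A formal paired comparison of the specimens would add little: under the same assumptions about 8 discordant pairs are expected, 700 × 0.005 × 2 × 0.8 × 0.2 = 1.1 in infected and 700 × 0.995 × 2 × 0.995 × 0.005 = 6.9 in uninfected subjects. For a pilot whose numbered objectives are an algorithm, its acceptability and its cost, such a test is a matter of preference.

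**Conclusion.** The concern does not call for a change to the plan. The observation is accurate, but it describes a definition left unwritten, not a wrong statement or a contradiction. Which test, specimen and phase define a descriptive rate is commonly settled in the statistical analysis plan, which may exist and is not shown. The harm requires a pooled screen-positive rate that the protocol does not announce, and its only explicit target for positivity is specific to Phase 1.

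The size cannot be determined from the protocol. Under the illustrative base values the pooled rate differs from the Phase 2 rate by 0 to 0.13 points and from the Phase 1 rate by 0 to 0.45 points, both within the sampling error of 12 events in 900. Lower specificity with independent errors would make the gaps larger. The conclusion therefore rests mainly on the absence of any commitment to pool, and on data that let analysts report by phase and specimen against RT-PCR, as they would naturally do. Writing the definition down would be a helpful minor clarification, nothing more.

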a) Passengers will purchase tickets directly from WestJet or KLM. On the day of departure, passengers will make their way to the check-in kiosk where they will go through the normal protocol of checking their bags. The airline staff will ensure that the passenger has minimum free time prior to their flight. If that is the case the staff member will inform them of Optional study conducted by UBC, WestJet, KLM and YVR - looking into the feasibility of a COVID-19 point-of-care rapid test device and algorithm for passenger management.

b) If the Passenger is interested, they will be directed to the Welcome Booth where they will meet a Study Coordinator and/or YVR staff. The Study Coordinator will provide each passenger with a welcome package consisting of 1) Simple study info sheet covering the purpose, the study plan, inclusion exclusion and potentiality of missing their flight if they participate; 2) A brochure with high-level details and frequently asked questions (see "General Brochure" in accompanying collateral document) 3) A water bottle; and 4) A pen which they will use for filling out the informed consent form and study questionnaire.

c) All passengers meeting the inclusion/exclusion criteria will be approached after checking bags. We will ensure that passengers have minimum required time prior to flight departure. If the subject is interested, they will be escorted to Informed Consent Area or the Citizen Care Pod for the full run through of the Informed Consent Form. After informed consent, we will start the process of sample collection.

Advance Recruitment

For WestJet passengers only, we will also recruit by sending an email at 72 hours pre-departure to WestJet guests who are flying out of Vancouver (see “WestJet Email to Guests”). The email will point to a WestJet microsite with further information on the study (see “WestJet Microsite”) and interested participants will be able to register in advance for the study at testingyvr.ca (see “Sign-up Microsite”). Those who choose to sign up in advance will receive a series of confirmation emails (see “Confirmation Emails”). Those signing up in advance must meet all the eligibility criteria and will follow the steps outlined above.

Details of Study Procedures

The study is purposefully designed to be as minimally invasive to the passengers’ travel plan as possible. The General Study Plan is detailed below.

Welcome Booth

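### Bottled water is handed out before the oral rinse is collected, and the protocol text does not ask participants to hold it until afterwards (minor)

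*Protocol*

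**What the plan says.** The water appears in two lists. The Welcome Booth section has "Welcome Package: bottled water, pens, brochure". Step b of Onsite Recruitment describes the same package and includes "3) A water bottle; and 4) A pen which they will use for filling out the informed consent form".

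An interested passenger is then sent to the consent area or the Citizen Care Pod, or may "wait inside terminal (5 seats allowing physical distancing with dividers". Step c of Onsite Recruitment says "After informed consent, we will start the process of sample collection", and the Citizen Care Pod section agrees: "Once signed consent form, proceed to collect NP swab and oral rinse".

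The section Rapid COVID-19 Testing On Site gives the use of each specimen. "For Phase 1, only the NP swab sample will be tested on site using the rapid test device", and then "The remaining NP swab sample and oral rinse sample will be transferred back to research laboratory for confirmatory RT-PCR testing". In Phase 2 both specimens go on rapid devices at the airport, a positive on either one counts as a positive screen, and what remains of both goes for RT-PCR.

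**The concern.** The written order puts a drink in the participant's hand, possibly seats them to wait, and then collects a specimen washed from the mouth. If some participants drink in that gap, there may be less oral material left for the rinse to pick up. Any such error would run one way, towards a negative rinse, and the NP swab is not exposed in the same way.

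The rapid test and the RT-PCR of the rinse use the same specimen. Material lost before collection would affect both, so the rinse RT-PCR could not be relied on to reveal a loss in the rinse rapid test. Because drinking is not recorded, no later analysis could separate its effect from the performance of the specimen itself.

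**Working it through.** The protocol gives no figure to reproduce here. The check is one of sequence and of which results the rinse feeds.

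**Order of steps**

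1. Welcome Booth: the package, including the water, is handed over before consent (Onsite Recruitment, step b; Welcome Booth). Step b alone could mean an empty bottle, but the Welcome Booth list makes clear that it is bottled water.
2. Possible wait on terminal seats, with no duration given (Welcome Booth).
3. Consent, then NP swab and oral rinse (Onsite Recruitment, step c; Citizen Care Pod).
4. Results Office: questionnaire and results, after sampling.

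The water therefore comes before the rinse.

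**Search for a safeguard**

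The sections from Onsite Recruitment to Data Collection contain no instruction on drinking, no interval before the rinse and no direction to staff to keep the water back. Personal Protective Equipment mentions rinse collection only as a step in the glove-and-gown sequence. The Data Collection list covers demographics, medical history and symptoms, but not recent drinking. The protocol ties the pen to a task at this stage (the consent form). It gives no reason for the water to come before sampling.

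**Which results could move**

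| Result | Phase 1 (200 planned) | Phase 2 (700 planned) |
|---|---|---|
| Rinse RT-PCR | exposed | exposed |
| Rinse rapid test | not done on site | exposed |
| NP rapid test | not exposed in the same way | not exposed in the same way |

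**When the screen result could change**

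In Phase 1 the screen rests on the NP rapid test alone, so it cannot change. In Phase 2 either positive is enough, which leaves four cases:

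| NP rapid test | Rinse rapid test if the participant had not drunk | Screen if the rinse is pushed to negative |
|---|---|---|
| positive | positive | still positive |
| positive | negative | still positive |
| negative | positive | **changes to negative** |
| negative | negative | still negative |

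Only one of the four cases is affected. Confirmation of a positive screen uses a newly taken NP swab (Positive Screen Test Results Protocol), so that step does not depend on the rinse.

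**Size**

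The exposure ceiling is 200 + 700 = 900 rinse specimens for RT-PCR and 700 for the rapid test. The protocol gives no rinse fluid, volume, technique, detection limit or sensitivity, and no share of participants who drink. No loss can be calculated from it.

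**The case against.** The strongest reply is that the mechanism is inferred. The rinse procedure is not described, and a rinse is itself liquid passed through the mouth, so what an earlier drink adds cannot be judged from the documents. Nothing says that participants drink before sampling: they are masked at the booth, and they go through the full consent form first, which takes an unstated time. An instruction could also sit in companion material that is not shown, such as the brochure, banners or confirmation emails. All of this stands. It limits the point to a plausible effect of unknown size, and it limits the missing instruction to the protocol text. It does not alter the order of steps, and the text that staff follow should not depend on what a leaflet may say.

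A reader might infer that infections would generally be missed at screening. The documents do not support that: the NP swab is still tested, and only the single Phase 2 case set out above changes. A reader might also infer that the rinse is tested on site straight after collection throughout; in Phase 1 it goes only to the laboratory. Nor is a comparison of rinse with NP swab a listed objective. The objectives are the screening algorithm, its acceptability and its cost, and the analysis is descriptive, with a positivity rate. A rinse that looked poor against the swab would therefore affect interpretation, not a planned test.

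**Conclusion.** The point holds as a minor one. The protocol places bottled water before oral rinse collection, and its text contains no instruction to hold it. If participants drink shortly beforehand, and if this clears or dilutes oral material, the rinse is pushed towards negative. Both conditions are assumptions, and no percentage can be attached to either.

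The consequence is confined to the rinse RT-PCR in both phases, the rinse rapid test in Phase 2, and those Phase 2 screens where the rinse alone would have been positive. The case for acting rests on three things: the error has a predictable direction, it cannot be separated afterwards, and it costs almost nothing to avoid. It does not rest on a demonstrated loss.

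**What to change.** Take the bottled water out of the package in both places where it is listed (Onsite Recruitment, step b, and Welcome Booth) and hand it out after sampling, at the Care Pod exit or the Results Office. The pen and brochure stay at the booth. Add one line at the booth asking participants not to drink until the rinse has been given; this also covers drinks that they bring themselves.

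Recording drinking is optional. If it is wanted, a yes/no item should be completed in the Care Pod after consent, not at the booth, where it would be collected before consent.

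The cost is a short wait for the water and a minor amendment, which under the protocol needs Research Ethics Board approval before use. The optional item adds one data field.
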